6.2 Handling of Dropouts or Missing Data

In order to achieve the goal of a well conducted clinical trial according to International Council on Harmonisation Good Clinical Practice, every effort should be made to collect all data (i.e., if a subject misses a scheduled assessment, the site personnel should contact the subject and request him/her to come to the clinic for the visit) (International Conference on Harmonisation, 1998; European Medicines Agency, 2011). However, despite best efforts, it may be inevitable that missing or incomplete data are reported. All missing or partial data will be presented in the subject data listings, as they were recorded on the eCRF.

Missing data will not be imputed in statistical analyses, except as noted below (Section 6.2.1 - 6.2.4).

6.2.1 Missing Dates

For AEs with partial or missing onset or stop dates:

AE stop date will be imputed first as:

- If stop date is completely missing, assume it is ongoing (no imputation);
- For a partial AE stop date: if day is missing, use last day of the month; if both day and month are missing, use December 31st.

Then AE onset date will be imputed as:

- If onset date is completely missing: the first dose date;
- For a partial AE onset date (day is missing, or both day and month are missing):
 - Partial date < the first dose date: last day of the month, or December 31st
 - Partial date = the first dose date: the first dose date
 - Partial date > the first dose date: first day of the month or January 1st

If the imputed AE onset date is after the AE stop date/imputed AE stop date, then the onset date will be set to the AE stop date/imputed AE stop date.

The imputed dates will not be listed. Study day relative to the first dose of study drug associated with missing or partial dates will not be displayed in AE listings.

In the event that a partial date (month/year or year) for concomitant medication is available, this information will be used as follows:

- When both month and year are available – first day of the month will be used for start date and the last day of the month will be used for the stop date.
- When only year is available – January 1st will be used for the start date and December 31st will be used for the stop date.

The imputed dates will only be used to determine whether a concomitant medication will be classified as prior medication or concomitant medication.

6.2.2 NASH CRN Histological Scores

Fibrosis scores are reported by the central histopathologist as 0, 1a, 1b, 1c, 2, 3, 4. Scores of 1a, 1b, and 1c will all be considered as fibrosis stage 1 for analysis. Worsening of fibrosis will be considered as an increase of 1 stage or more. Note that the baseline fibrosis score (F1 vs. F2/F3) to be included as a factor in the logistic regression, risk differences, and ANCOVA models will be the value used to determine the stratum at randomization and will come from the IXRS. The categorical fibrosis score summarized with counts and percentages and as a numeric score in the demographic summary, as well as the analyses of fibrosis score as a numeric endpoint will use those values reported by the central histopathologist as follows:

- In case the liver biopsy was repeated due to a clinical reason as determined by the investigator and approved by Cirius, or because the sample was not readable the biopsy with the latest collection date will be used.
- In case there are multiple samples (accession numbers) associated with a biopsy on a given collection date, the results for the accession number associated with the highest NAS will be used for analysis.
- Results from the central histopathologist's blinded reread of the qualifying screening biopsy utilized to determine eligibility will be used as baseline data.

The NASH CRN histological scores as read by the local pathologist and recorded on the eCRF at Screening (BIOPFIB1) and at Visit 7 (BIOPFIB2) will not be used in any analyses but may be included in subject listings.

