5.2 Modified Intent-to-treat Analysis Set

The modified Intent-to-Treat (mITT) analysis set includes all subjects who are randomized and who receive at least one dose of study drug. Baseline measures and post-baseline assessments through 14 days after the last dose of study drug will be included in the analyses unless stated otherwise below. Subjects in the mITT will be analyzed as randomized regardless of treatment received. This means that subjects who are randomized who receive the incorrect study drug (i.e., not the study drug to which they were randomized) will be analyzed for efficacy under mITT as in the treatment group to which the subject was randomized. The primary population for efficacy analyses is the mITT.

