7.8 Efficacy

7.8.1 Primary Efficacy Analysis

The primary efficacy endpoint is hepatic histological improvement in NAS (NASH CRN scoring). A responder (subjects with hepatic histological improvement) is defined as having all of following:

- A decrease of at least 2 points in NAS at 12 months. The reduction in NAS must also include at least a 1 point reduction in either ballooning or inflammation.
- No worsening of fibrosis, defined as no increase in CRN fibrosis score of ≥ 1 stage.

Each MSDC-0602K dose group will be compared with the placebo group at the two-sided 0.05 significance level. For each comparison, the null hypothesis is that there is no difference in response rates between the MSDC-0602K dose and placebo. The alternative hypothesis is that there is a difference in response rates between the MSDC-0602K dose and placebo. The primary analysis of the primary efficacy endpoint will be performed in the mITT population, with supportive analysis in the PPS population. The number and percentage of responders will be summarized by treatment group. Analyses of liver biopsy findings will be based on the central expert histopathologist's repeat read of the Screening biopsy and read of the Visit 7 biopsy. The central read of the Screening biopsy for purposes of determining subject eligibility, and the local pathologist's assessments, will not be considered for these analyses. Covariate adjustment for randomization stratification factors diabetes mellitus, baseline fibrosis (F1 versus F2/F3), and vitamin E use will utilize values reported at randomization and which determined the stratum in which the subject was randomized.

The primary analysis will be conducted using observed data included in the analysis dataset. Five additional sensitivity analyses will be conducted in the mITT population where (1) missing values are multiply imputed, (2) subjects with missing data will be treated as non-responders, as outlined in Section 6.2.3, (3) subjects with biopsy results up to and including (\leq) 1 day after last dose of study drug will be included, (4) subjects with biopsy results up to ($<$) 7 days after last dose of study drug will be included, and (5) all observed data will be used (including biopsy results obtained more than 14 days after last dose of study drug). These sensitivity analyses will include all subjects who were randomized and who received at least one dose of study drug.

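### SAP 6.2.2 picks among several biopsy samples by the highest NAS, and its latest-date rule for repeat biopsies conflicts with SAP 6.1 and has no stated order against the 14-day limit

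*SAP*

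**What the plan says.** SAP 6.2.2 (NASH CRN Histological Scores) contains two selection rules.

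- Several samples from one collection date: "the results for the accession number associated with the highest NAS will be used for analysis".
- Repeat biopsies: "In case the liver biopsy was repeated due to a clinical reason as determined by the investigator and approved by Cirius", or, as a separate alternative, "because the sample was not readable the biopsy with the latest collection date will be used". A clinical reason is therefore enough by itself; the first biopsy need not have been unreadable.

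The sentence that introduces these rules covers the fibrosis summaries, "as well as the analyses of fibrosis score as a numeric endpoint will use those values reported by the central histopathologist as follows". It does not name NAS or its components. A third bullet fixes the baseline source: "blinded reread of the qualifying screening biopsy utilized to determine eligibility will be used as baseline data".

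Three other places bear on the point.

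- SAP 7.8.1 defines a responder first by "A decrease of at least 2 points in NAS at 12 months". It also requires a ballooning or inflammation component to fall and fibrosis not to worsen.
- SAP 6.1 prefers scheduled to unscheduled data after baseline when both carry the same nominal visit.
- SAP 5.2 limits the mITT analysis: "post-baseline assessments through 14 days after the last dose of study drug will be included in the analyses".

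None of the five additional mITT sensitivity analyses in SAP 7.8.1 varies which sample or which biopsy is used. They vary missing-data handling and the time window.

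**The concern.** The higher of two noisy scores is, on average, above the true value. Applied to a baseline biopsy, this makes a later fall of 2 points easier to reach without any change in the liver. Applied to a month-12 biopsy, it hides real falls. The analysed score then depends partly on how many samples happened to be processed. Fibrosis is read from whichever sample had the highest NAS, and that sample need not have the highest fibrosis stage.

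The repeat-biopsy rule raises a different problem. The SAP does not define a clinical reason, does not require the decision to precede knowledge of the first result, and sets no time limit on the repeat. A readable month-12 biopsy can be displaced, and two other SAP rules give, or may give, a different answer about which biopsy counts.

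At stake are the level of the response rates, a small amount of power, and the status of any subject who has two month-12 biopsies.

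**Working it through.** **Step 1: the plan's own figure.** Inputs from SAP 2.3: 85 per arm, 20% versus 39.5%, two-sided 0.05, 10% dropout. With pooled rate 0.2975:

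power = Φ[(0.195 − 1.96·√(2·0.2975·0.7025/85)) / √((0.20·0.80 + 0.395·0.605)/85)] = Φ[(0.195 − 0.1374)/0.0685] = Φ(0.840) = 0.800.

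For the total, 340/0.9 = 378 against the stated 380. The design figure reproduces and is not in dispute.

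**Step 2: a stable subject.** The documents give no between-sample SD, so s is assumed. Let the true NAS t be the same at both visits and spread evenly over 4.5 to 5.5, with integer scores. For one sample P(score ≤ k) = Φ((k + 0.5 − t)/s); for the higher of two, this probability is squared. The chance of an apparent fall of 2 or more points, averaged over t, is:

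| s | one sample at each visit | higher of two at baseline only | higher of two at month 12 only | higher of two at both |
|---|---|---|---|---|
| 0.5 | 2.5% | 4.4% | 0.5% | 1.0% |
| 0.7 | 7.3% | 12.3% | 2.2% | 4.2% |
| 0.9 | 12.5% | 20.4% | 4.6% | 8.4% |

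The mean score rises by s/√π = 0.56s, that is 0.28 to 0.51 points. Per 10% of stable subjects with duplicates at baseline only, the shift is 0.10 × (4.4 − 2.5) = 0.2 to 0.10 × (20.4 − 12.5) = 0.8 percentage points upward. It is about the same size downward for month 12 only.

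Two patterns do not raise the rate. Equal frequency in different subjects averages back to the single-sample value: for s = 0.7, (12.3 + 2.2)/2 = 7.25, against 7.3. Duplicates at both visits in the same subject make a false fall less likely (4.2% against 7.3%).

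**Step 3: on the scale of the design.** This is a simulation of the NAS part of the endpoint only. Assumptions: latent baseline NAS mean 5.3 and SD 1.0, held within 3 to 8; SD of change 1.0; s of 0.5, 0.8 or 1.0; two samples where duplicated; mean change set so that single-sample rates are 20% and 39.5%.

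- Baseline only, 10% to 30% of subjects: placebo 20.6% to 22.6%, active 40.4% to 43.1%, power 80.5% to 82.3%.
- Month 12 only, 10% to 30%: placebo 19.3% down to 17.3%, active 38.6% down to 35.6%, power 80.1% down to 77.9%.
- Equal frequency at both visits, 10% or 30%: placebo 19.6% to 20.0%, active 39.2% to 39.5%, power 80.0% to 81.5%.

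**Step 4: the repeat rule beside its neighbours.** Take a subject with a readable Visit 7 biopsy within 14 days of last dose and an unscheduled clinical-reason repeat assigned to the same visit.

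- SAP 6.2.2 selects the repeat; SAP 6.1 selects the scheduled biopsy. No precedence is stated.
- If the repeat falls more than 14 days after last dose, order matters. With the 14-day filter first, the in-window biopsy is the only one left and the subject is analysed. With the latest-date rule first, the repeat is chosen and then excluded.
- In that second case the observed-data primary analysis loses the subject, the non-responder analysis counts a failure, and multiple imputation replaces a result that exists. The all-observed analysis brings back the repeat, not the first biopsy.

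**The case against.** The rules are written in advance, and the sample rule is mechanical. Protocol 7.7 has slides blinded for subject and visit before central reading, baseline is a blinded reread, and the trial is double-blind. The sample rule names no visit, so it applies at both, where its effects tend to cancel. Even 30% duplication at month 12 alone leaves power near 78%. Taking NAS and fibrosis from one sample is coherent. All of this stands.

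A reader might infer that the highest-NAS rule favours active drug or inflates type I error. The documents do not support that. Under the step 3 assumptions with no true effect, type I error rises to 0.051 to 0.062 only if month-12 duplicates are more frequent in one arm (10% against 0%, or 30% against 10%). Nothing suggests such a difference under blinding.

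A reader might also infer that the sponsor picks between two known results. The text requires a clinical reason determined by the investigator; discretion lies in the decision to repeat, after which the latest date is a fixed rule. At baseline, the qualifying-biopsy bullet limits the room further.

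Finally, it may be said that the lead-in confines the rules to fibrosis. Literally it does. But the section heading covers all histological scores, the rule selects on NAS, and no other sample rule for NAS exists. On the narrow reading, the secondary endpoint of mean change in fibrosis is still affected, and NAS is left with no rule at all.

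**Conclusion.** The SAP should not select an endpoint sample by the score that defines the endpoint, and its rules for repeat biopsies need one stated order. That much follows from the text.

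The effect on results is conditional. A shift in response rates needs duplicates to be more frequent at one visit than at the other, and it then moves all arms in the same direction. With assumed SDs of 0.5 to 1.0 and one-visit duplication of 10% to 30%, it is about 0.6 to 2.7 percentage points for placebo, against a design difference of 19.5 points. Real frequencies could lie outside that range, since the documents give neither quantity. The illustration also ignores the component and fibrosis conditions of the responder definition.

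Loss of a valid in-window biopsy is a possible outcome of the wording, not a certain one. It needs a readable first biopsy, a clinical-reason repeat beyond 14 days, and the latest-date rule applied first. The conflict with SAP 6.1 for an unscheduled month-12 repeat needs none of the timing assumptions.

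**What to change.** Amend SAP 6.2.2 before unblinding:

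1. State that the rules cover NAS, its components and fibrosis.
2. Choose among several samples without regard to score, in the same way at both visits: by recorded adequacy if this is held for each accession number, otherwise the first accession number.
3. At month 12, analyse the first readable biopsy within the 14-day limit, and a repeat only if the first was unreadable. This concerns which result is analysed, not whether a subject has a repeat.
4. State that this takes precedence over the scheduled-first rule of SAP 6.1.
5. Report counts of multiple samples and repeats by arm and visit.
6. Keep the highest-NAS and latest-date rules as a sensitivity analysis.

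The cost is SAP wording and a little extra analysis; the sample size does not change. The fallback needs no new reads, because the highest-NAS rule already requires every sample to be scored. Adequacy may not be available: Protocol 7.7 gives core length and portal tracts as a recommended procedure and does not say that the reader records them for each sample. The first-accession fallback is arbitrary, but it does not depend on the score.

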6.2.3 Imputation for Primary Endpoint

Sensitivity analyses will be performed on the primary endpoint using two different imputation methods. The sensitivity analyses will include all subjects who were randomized and who received at least one dose of study drug. Two approaches will be used to impute or substitute missing response at 12 months. Post-baseline observations that have been excluded from the primary analysis due to biopsies taken more than 14 days after last dose of study drug will be treated as missing and imputed or substituted as well.

When using multiple imputation, missing baseline and/or post-baseline values needed to determine response at 12 months will be imputed multiple times to account for the uncertainty about the true values to impute. To this end, each of the four categorical variables underlying the response definition of the primary endpoint will be imputed if missing, using the following categories:

- Steatosis: 0, 1, 2, 3
- Lobular inflammation: 0, 1, 2, 3
- Ballooning: 0, 1, 2
- Fibrosis score: 0, 1, 2, 3, 4

Using the SAS[®] procedure PROC MI 10 imputed data sets will be generated. The regression model will be adjusted for the corresponding baseline values and will further use presence of diabetes mellitus, Vitamin E use ≥ 400 IU, age, and sex as covariates.

An example of the SAS[®] code to be used is below:

```
proc mi data= out=<output dataset> seed=1234 nimpute=10
  minimum=<...> maximum=<...> round=<...>;
var <12 months steatosis> <baseline steatosis>
  <12 months lobular inflammation> <baseline lobular inflammation>
  <12 months ballooning> <baseline ballooning>
  <12 months fibrosis score> <baseline fibrosis score>
  <presence of diabetes mellitus> <Vitamin E use  $\geq 400$  IU> <sex><age at baseline>;
run;
```

The 10 multiple imputed datasets will be used separately in the statistical analysis model and the resulting odds ratios and 95% CIs will be combined via Rubin's rules (using PROC MIANALYZE) to provide a global estimate of the odds ratio with a corresponding 95% CI and p-value.

As a second sensitivity analysis of the primary endpoint, subjects with missing response data at 12 months will be included as non-responders. Similar to above, this sensitivity analysis will include all subjects who were randomized and who received at least one dose of study drug.

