7 STATISTICAL METHODS

7.1 General Principles

All data processing, summarization and analyses will be performed using Version 9.3 (or later) of the SAS® (SAS Institute, Cary, NC) statistical software package.

Unless specified otherwise, data will be displayed using the following treatment group labels, in the order presented:

- Placebo
- MSDC-0602K 62.5 mg
- MSDC-0602K 125 mg
- MSDC-0602K 250 mg
- Total (if applicable)

All data collected will be presented in listings by treatment group, site, subject, and visit (where applicable), unless otherwise specified.

Data will be presented in summary tables by treatment group, assessment and visit (where applicable).

Descriptive summary statistics for continuous variables will include the number of observations (N), mean, standard deviation (SD), median, 25th and 75th percentiles, minimum and maximum.

Descriptive summary statistics for categorical variables will include frequency counts and percentages [n (%)]. Unless stated otherwise in the table shells, the denominator for percentage calculations will be the number of subjects in the analysis population with a non-missing value.

Dates will be displayed as DDMMYYYY.

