Comparisons between each active treatment group and the placebo group will be evaluated using appropriate contrasts from a logistic regression model including treatment and adjusted for presence of diabetes mellitus, baseline fibrosis F1 versus F2/F3, and ordinal baseline NAS. Model-adjusted odds ratios for each active dose group relative to placebo and their associated 95% confidence intervals (CIs) and p-values will be provided.

In addition, stratification-adjusted differences in response rates (risk differences) adjusted for presence of diabetes mellitus, baseline fibrosis F1 versus F2/F3, and ordinal baseline NAS between each active dose group and placebo and their associated 95% CIs and p-values will be provided (LaVange et al 2005; Zink and Koch 2012).

Statistical Analysis Plan

Version: Final 1.5

Date of Issue: 16-May-2019

Cirius Protocol No. MSDC-0602K-C009NASH

Supportive analyses of the primary endpoint will include comparisons of each active dose group with placebo using Cochran-Mantel-Haenszel (CMH) tests stratified by presence of diabetes mellitus.

Sensitivity analysis for the primary endpoint will be performed using a logistic regression model including treatment and adjusting for presence of diabetes mellitus, baseline fibrosis F1 versus F2/F3, sex, age, and ordinal baseline NAS. Adjusted odds ratios relative to placebo and the corresponding 95% CIs and p-values will be provided.

A summary of the planned primary efficacy analyses is given below:

Method	mITT Observed data	PPS Observed data, data exclusions possible due to non-compliance	mITT Multiply imputed response data	mITT Missing response status at 12 months set to non-responder	mITT Observed data ≤1 day after last dose of study treatment	mITT Observed data <7 days after last dose of study treatment	mITT Observed data including results any time after last dose of study treatment
Logistic regression (odds ratios) including treatment group and adjusted for presence of diabetes mellitus, baseline fibrosis F1 versus F2/F3, ordinal baseline NAS.	X*	X	X	X	X	X	X
Stratification-adjusted differences in response rates (risk differences) between each active dose group and placebo adjusted for presence of diabetes mellitus, baseline fibrosis F1 versus F2/F3, ordinal baseline NAS.	X	X	X	X	X	X	X
CMH tests of each active dose group versus placebo stratified by presence of diabetes mellitus.	X	X					

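### No planned primary-endpoint analysis both uses every month-12 biopsy and counts every treated subject; the gap is small there and wider for the two binary secondary endpoints

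*SAP*

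**What the plan says.** The primary analysis uses observed biopsies in the mITT set, for which SAP 5.2 says that "post-baseline assessments through 14 days after the last dose of study drug will be included in the analyses unless stated otherwise below". Protocol 11.2 sets the same 14-day limit.

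SAP 7.8.1 adds five sensitivity analyses: (1) multiple imputation, (2) missing counted as non-response, (3) biopsies no more than 1 day after last dose, (4) biopsies less than 7 days after last dose, and (5) all observed biopsies.

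- For (1) and (2), SAP 6.2.3 says that "biopsies taken more than 14 days after last dose of study drug will be treated as missing and imputed or substituted as well".
- For (5), SAP 7.8.1 reads "5) all observed data will be used (including biopsy results obtained more than 14 days after last dose of study drug". Its column in the summary table is labelled "Observed data including results any time after last dose of study treatment".
- The general rule in SAP 6.2 is "Missing data will not be imputed in statistical analyses, except as noted below". The only exception that concerns biopsy response is 6.2.3, which covers the primary endpoint and only the methods of (1) and (2).
- After listing the five analyses, SAP 7.8.1 adds: "These sensitivity analyses will include all subjects who were randomized and who received at least one dose of study drug".

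On the imputation model, SAP 6.2.3 says "The regression model will be adjusted for the corresponding baseline values and will further use presence of diabetes mellitus", followed by vitamin E use, age and sex. Neither that list nor the example code contains treatment arm.

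For NASH resolution and fibrosis improvement, SAP 7.8.2 plans observed-data analyses with several biopsy windows, including all observed data. It plans no imputation and no non-responder analysis.

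**The concern.** Two kinds of subject can be missing from the primary analysis: those biopsied long after stopping drug, and those never biopsied. The protocol's own rules can produce both. Subjects stopped for some reasons are told to continue visits (Protocol 6.4, 6.6), and refusing drug is not withdrawal of consent (6.3), so they can reach the Visit 7 biopsy. Subjects who withdraw consent are instead asked for an evaluation equivalent to Visit 8 (6.3), and the Visit 8 procedure list has no biopsy (6.2.10).

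Analyses (2) and (5) each relax one feature of the primary analysis. When some who stop are biopsied and others are not, neither shows the result with both features relaxed. If the share biopsied differs by arm, that result need not lie between them. For the two binary secondary endpoints the stake is plainer: every planned estimate rests only on subjects who have a biopsy.

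**Working it through.** **1. The plan's own figure.** Inputs from SAP 2.3: 85 per arm, 39.5% versus 20%, two-sided 0.05. The mean rate is 0.2975. The pooled SE is √(2×0.2975×0.7025/85) = 0.0701, and the unpooled SE is √((0.395×0.605 + 0.20×0.80)/85) = 0.0685. Then z = (0.195 − 1.96×0.0701)/0.0685 = 0.84, giving power of 79.96%. The stated 80% reproduces. With 10% dropout, 340/0.90 = 378, against about 380 planned.

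**2. Each planned primary-endpoint analysis against two criteria.**

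| Analysis | Uses every collected biopsy | Counts every treated subject |
|---|---|---|
| Primary (mITT, observed) | no | no |
| Per-protocol | no | no |
| (1) Multiple imputation | no | yes |
| (2) Non-responder | no | yes |
| (3) ≤1 day, (4) <7 days | no | no |
| (5) All observed | yes | no |

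None meets both. For the binary secondary endpoints there is no row like (1) or (2), so the right-hand column is always no.

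**3. Illustrated size for the primary endpoint.** Let s be the share stopping drug, b the share of those biopsied, and r the off-drug response; A is active and P is placebo. Assumptions: 39.5% on drug, 20% on placebo, r = 20% in both arms, every on-drug subject has an evaluable biopsy, and every biopsied stopper is beyond 14 days. The values of s and b are assumed.

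- Planned (2) = 0.395(1−sA) − 0.20(1−sP)
- Combined (all biopsies, none counted as non-response) = [0.395(1−sA) + rA·sA·bA] − [0.20(1−sP) + rP·sP·bP]
- Planned (5) = the same two bracketed terms, each divided by (1−s+s·b) for its arm
- Primary = 39.5 − 20 = 19.5 points throughout

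Worked case, 20%/10% stopping, half biopsied: combined 33.6 − 19.0 = 14.6; planned (2) 31.6 − 18.0 = 13.6; planned (5) 33.6/0.90 − 19.0/0.95 = 17.3.

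| Stopping A/P | Biopsied A/P | Combined | (2) | (5) | Combined − (2) |
|---|---|---|---|---|---|
| 10/10% | 50/50% | 17.6 | 17.6 | 18.5 | 0 |
| 20/10% | 50/50% | 14.6 | 13.6 | 17.3 | +1.0 |
| 15/5% | 50/50% | 15.6 | 14.6 | 17.9 | +1.0 |
| 10/20% | 50/50% | 18.6 | 19.6 | 18.5 | −1.0 |
| 15/15% | 25/75% | 15.1 | 16.6 | 18.7 | −1.5 |
| 15/15% | 75/25% | 18.1 | 16.6 | 17.2 | +1.5 |

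The last column is the effect of the late-biopsy rule on the non-responder result, rA·sA·bA − rP·sP·bP. Over 10–20% stopping and 25–75% biopsied in each arm, its extreme is 0.20×(0.20×0.75 − 0.10×0.25) = 2.5 points, in either direction. If active subjects kept 39.5% response off drug (20%/10%, half biopsied), it would be 0.395×0.20×0.50 − 0.20×0.10×0.50 = 2.95 points.

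For scale, with 380/4 = 95 per arm and rates of 33.6% and 19.0%, the SE of a difference is √((0.336×0.664 + 0.190×0.810)/95) = 6.3 points. A shift of 2.5 is about 0.4 of that.

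**4. Imputation without an arm term** (approximate, ignoring covariates). At 20%/10% stopping with all three doses at 39.5%, missing responses in every arm are drawn near (3×0.8×0.395 + 0.9×0.20)/(3×0.8 + 0.9) = 34.2%. The active rate becomes 0.8×39.5 + 0.2×34.2 = 38.4% and the placebo rate 0.9×20 + 0.1×34.2 = 21.4%. The difference is 17.0 points, against 19.5 if each arm were imputed at its own observed rate.

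**The case against.** The case against acting is substantial. The summary table already has seven data columns. The 14-day limit comes from the protocol and is openly stated. The objective is a preliminary assessment, and neither document requires the combined analysis. That analysis is also a hybrid, since an off-drug biopsy counts as observed while an absent one counts as failure. At the plan's nearest figure, 10% non-completion, equal stopping and equal biopsy uptake give no effect on the non-responder result. Once the 19.5-point primary is included, the 75%/25% case falls inside the planned range. The 25%/75% case needs a threefold difference in biopsy uptake between blinded arms, which nothing in the documents suggests. All of this stands, and it keeps the point minor.

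The sentence "These sensitivity analyses will include all subjects who were randomized and who received at least one dose of study drug" could be read as already making (5) count everyone. It does not close the gap. It cannot be literally true of (3) and (4), which are defined by having a biopsy inside a window, and it gives (5) no outcome for a subject without one.

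The rule in SAP 7.1 that "the denominator for percentage calculations will be the number of subjects in the analysis population with a non-missing value" is only weak support for saying such subjects drop out. It yields to table shells that are not in the documents, and it concerns descriptive percentages. The argument rests on SAP 6.2 and the table label instead.

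**Conclusion.** The gap is real and minor. It is wider for NASH resolution and fibrosis improvement, where no planned analysis counts treated subjects without a biopsy; the documents give no response rates there, so no size is offered. For the primary endpoint the illustrated effect of the late-biopsy rule is 0 to about 2.5 points either way. Of the six cases shown, only unequal uptake of 25%/75% puts the combined result (15.1) outside all of (2), (5) and the primary (16.6, 18.7, 19.5). With no biopsies beyond 14 days, the rule has no effect. Unreadable on-drug biopsies, which SAP 6.2.2 foresees, would change the figures.

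A reader might infer that the 14-day rule is an error, that the primary result is biased in a known direction, or that (2) and (5) generally fail to bracket the combined result. The documents support none of these. The rule follows Protocol 11.2, stopping and late-biopsy rates are not given, and failure to bracket needs a particular imbalance.

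**What to change.** (a) In SAP 7.8.2, add for both binary secondary endpoints a named sensitivity analysis that uses every collected month-12 biopsy regardless of time since last dose and counts treated subjects with no evaluable biopsy as non-responders.

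(b) Add the same analysis for the primary endpoint in SAP 7.8.1, with a column in the summary table.

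(c) Amend SAP 6.2 and 6.2.3 to permit it; otherwise the new analysis would conflict with both. Limit the all-subjects sentence in 7.8.1 to (1), (2) and the new analysis. Say whether the site exclusions allowed in SAP 5 apply to it. Record the change in Section 8.

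(d) Include treatment arm in any multiple-imputation model, including planned analysis (1).

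SAP 5.2 already allows stated departures from the 14-day limit, so no protocol amendment or new data are needed. The primary analysis and its power do not change. The cost is a little more analysis work and possibly a less favourable sensitivity estimate. The edits belong before final unblinding; if that has passed, the analysis should be labelled post hoc.
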